**T-Test Example Code:**

```
ods output conlimits = conlimits ttests = ttests;  
proc ttest data = adeff dist = normal sides = 2 ci = equal alpha = 0.05;  
class trtan;  
var aval;  
run;
```

**Presentation of Results**

Linear mixed effects model approach:

- Estimation of mean and 95% CI for both groups:
  - Point Estimate: Estimate Variable in lsmeans dataset
  - Corresponding 95% CI: Lower vs. Upper variables in lsmeans dataset
- Estimate and 95% CI for difference in means between groups:
  - Filtered all TRT A N ≠ TRT A N and AVISITN = AVISITN records in Diffs dataset and output:
    - Point Estimate: Estimate Variable in Diffs Post-Screening Dataset
    - Corresponding 95% CI: Lower versus Upper Variables in Diffs Post-Screening Dataset
- P-value: Probt variable in filtered dataset Diffs

T-Test:

- The difference in means and 95% CI are available from CONFLIMITS.
- P-values for t-tests are available from TTESTS.

## 9.2 Safety analyses

### 9.2.1 Overview of Planned Safety Analyses

Unless otherwise stated, safety analyses will be based on the Safety Analysis Set.

Table 7 provides an overview of the planned safety analyses.

**Table 7 Planned Safety Analysis Overview**

	Data Presentation Generated		
	Table	Figure	Listing
Adverse events (within 90 days/360 days after surgery)			
All Adverse Events	Y		Y
Serious Adverse Events (SAEs)			
Moderate and severe adverse events			
Procedure-related serious complications within 30 days after randomization (including surgical and interventional procedures)			
Major complications associated with drilling or MMA embolization	Y		Y
Major complications associated with drilling			
Major complications associated with MMA embolization			
Adverse events of special interest			
Adverse events of special interest	Y		Y
Serious adverse events of special interest			Y
Death (within 90 days/360 days after randomization)			
Death from any cause	Y		Y
Concomitant medications			
Antiplatelet or anticoagulant therapy	Y		Y
Other concomitant medications			

Notes:

1. Categorical data.
2. Postoperative serious complications include: symptomatic intracranial hemorrhage, surgery-related intracranial hemorrhage, surgery-related neurological dysfunction, surgery-related central nervous system infection, surgery-related arterial dissection, vessel wall injury, and vessel rupture and perforation, surgery-related ischemic events, retroperitoneal/wrist hematoma, puncture site neuropathy, contrast agent allergy, or contrast agent encephalopathy

Y = Plan Generation.

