3.1 Overall Study Design

This is a multicenter, phase III, prospective, randomized, open-label, and parallel controlled clinical study with blinded outcome assessment. Approximately 722 cases will be included in this study in China, with a ratio of 1:1 for randomization into the MMA embolization and

traditional treatment groups.

The study phases include: 1) Screening and baseline period: confirm whether patients are eligible for the study and create a record; decide whether trepanation and drainage should be performed by considering the condition of the disease and the imaging results; carry out randomized assignment and therapy. Eligible subjects will be randomly assigned to the traditional treatment group or MMA embolization group at a ratio of 1:1. 2) Follow-up period: visit patients for efficacy endpoints and safety endpoints at 30 days, 90 days, and 360 days post-procedure.

Figure 1. Schematic diagram of inclusion and randomization of subjects

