7.1.3 Estimation of sample size

This study hypothesizes that MMA embolization may reduce the recurrence (operation group) or progression (conservative treatment group) of SDH. The estimated recurrence or progression rate of hematoma in the MMA embolization group is 5%, while that of control group is 12%. When estimating bilateral 5% for the statistical significance level, 90% for power, and 8% for an acceptable rate of loss to follow-up, the total sample size is estimated to be 722 cases.

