10.2 SAEs

SAEs are the following events occurred during the clinical study:

- 1) Death;
- 2) Fatal disease or injury;
- 3) Permanent impairment of a body structure or a body function;
- 4) Resulting in hospitalization or prolonged hospitalization;
- 5) Medical or operative intervention is required to avoid any permanent impairment in the physical structure or physical function;
- 6) Fetal distress, fetal death or congenital anomalies, congenital defect, etc.

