
 
To validate the safety of MMA embolization with liquid embolic materials
 
	
 
Serious Adverse Events (SAEs) within 90 days and 360 days
 
Death within 90 days and 360 days
 
Severe surgery-related complications within 30 days after surgery (including trepanation/drainage and MMA embolization): 
 
Symptomatic intracranial hemorrhage
 
Surgery-related intracranial hemorrhage
 
Surgery-related neurological deficits
 
Surgery-related central nervous system infection
 
Surgery-related arterial dissection, vascular wall injury and vascular rupture and perforation
 
Surgery-related ischemia
 
Access site hematoma
 
Neuropathy at the puncture site
 
Contrast allergy or contrast encephalopathy
 
 
 

 
To validate the reduction of residual hematoma at 90 days after randomization in patients
 
	
 
Changes of hematoma thickness on CT/MRI imaging at 90 days after randomization
 

Study objectives	Study Endpoints
undergoing MMA embolization	
 
Changes of hematoma volume at 90 days after randomization
 
Changes of midline shift in CT/MRI imaging at 90 days after randomization
 

 
To validate the improvement in clinical outcome (mRS score) at 90 days and 360 days after randomization in patients undergoing MMA embolization
 
	
 
Changes of Modified Rankin Scale (mRS) score at 90 days and 360 days after randomization
 
Proportion of patients with mRS score of 0 to 2 at 90 days and 360 days after randomization
 
Proportion of patients with mRS score of 0 to 3 at 90 days and 360 days after randomization
 

 
To validate the improvement in health status (EQ-5D-5L scale) at 90 days and 360 days after randomization in patients undergoing MMA embolization
 
	
 
Quality of life evaluated with EQ-5D-5L Scale at 90 days and 360 days after randomization
 

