### **3. Sample Size Considerations**

The study hypothesizes that patients undergoing middle meningeal artery embolization may have lower symptomatic recurrence (in the trepanation/drainage group) and lower rates of symptomatic hematoma progression (in the non-surgical group) of subdural hematoma compared to patients who do not go MMA embolization. Two interim analyses will be conducted. With an expected symptomatic recurrence rate (trepanation/drainage group) / symptomatic progression rate (non-surgical group) after MMA embolization of 5% compared with 12% in the control group, and considering a loss to follow-up rate of 8%, a sample size of 722 cases with a two-sided alpha of 0.05 would yield 90% power.

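### Admissions and operations for SDH recurrence or progression will often count as SAEs, and the plan has no by-arm SAE count without them, so a primary-endpoint benefit can partly offset a procedural excess in the total SAE rate

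*SAP*

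**What the plan says.** Protocol 10.2 lists what makes an event serious. Two criteria matter here: "Resulting in hospitalization or prolonged hospitalization" and "Medical or operative intervention is required to avoid any permanent impairment". Neither exempts efficacy events. SAP 9.2.2.1 counts an untoward occurrence as an adverse event whether or not it is related to the device.

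Under protocol section 2 the primary event includes re-operation in the surgical stratum and operation in the drug-therapy stratum. SAP 8.2.1 adds that a record of such surgery settles the endpoint without imaging or symptoms. Protocol 7.3.1 also counts death from any cause within 90 days as a primary event, and death is an SAE.

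SAP 1.2 sets SAEs within 90 and 360 days as a safety endpoint, and Table 7 gives them a row, "Serious Adverse Events (SAEs". Table 7 also has rows for 30-day serious complications (drilling, embolization, and either), special-interest events and death. SAP 9.2.2.1 plans frequency tables by system organ class and preferred term. No passage in the available text plans an SAE count that leaves out recurrence and progression.

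**The concern.** A patient admitted or operated on for recurrence or progression would ordinarily meet an SAE criterion. The control arm is expected to have more such patients, so its SAE total should be higher for reasons that have nothing to do with the safety of the procedure.

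Two things follow for a trial with a stated objective of validating the safety of embolization:

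- If the procedure causes no serious harm, the SAE total still favours embolization and shows the efficacy result a second time as a safety result.
- If the procedure does cause serious harm, the avoided recurrences offset some of it, and the totals can look similar.

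**Working it through.** **Inputs from the documents**

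- Event rates, protocol 7.1.3: "The estimated recurrence or progression rate of hematoma in the MMA embolization group is 5%, while that of control group is 12" (per cent).
- Size and power, SAP section 3: "a sample size of 722 cases with a two-sided alpha of 0.05 would yield 90% power".
- Loss, SAP section 3: "considering a loss to follow-up rate of 8" (per cent).
- Allocation, protocol 3.1: "Eligible subjects will be randomly assigned to the traditional treatment group or MMA embolization group at a ratio of 1:1", so 722/2 = 361 per arm.

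**Assumed, because the documents do not give them**

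- b, the proportion of patients per arm with other SAEs: 5–15%.
- f, the share of primary events that are also SAEs: 25–100%.
- Other SAEs and primary events are independent.

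**The plan's own figure.** The two-sided normal approximation with pooled variance under the null and 90% power gives n = [1.960·√(2·0.085·0.915) + 1.282·√(0.12·0.88 + 0.05·0.95)]² / 0.07² = 332 per arm, 664 in total. 664/0.92 = 722, so the sample size reproduces exactly.

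**Expected primary events.** 361 × 0.12 = 43 and 361 × 0.05 = 18, a gap of about 25 patients.

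**Model.** Let h be the excess procedural SAE rate in the embolization arm.

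- Control SAE rate = 1 − (1 − b)(1 − 0.12f)
- Embolization SAE rate = 1 − (1 − b − h)(1 − 0.05f)

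Setting the two equal gives the excess that is exactly offset: h = (1 − b) × 0.07f / (1 − 0.05f). For f = 0.5 and b = 5%, this is 0.95 × 0.035/0.975 = 3.41 points.

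| f | h at b = 5% | b = 10% | b = 15% | patients per 361 |
|---|---|---|---|---|
| 25% | 1.68 | 1.59 | 1.51 | 5.4–6.1 |
| 50% | 3.41 | 3.23 | 3.05 | 11.0–12.3 |
| 75% | 5.18 | 4.91 | 4.64 | 16.7–18.7 |
| 100% | 7.00 | 6.63 | 6.26 | 22.6–25.3 |

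**No procedural harm (h = 0, b = 10%).** Control v embolization SAE rates are 12.7% v 11.1% at f = 25%, 15.4% v 12.3% at 50%, and 20.8% v 14.5% at 100%.

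**True excess of 5 points (b = 10%).** Power is for an illustrative two-sided 5% comparison at 361 per arm; SAP 9.2 specifies no such test.

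| Count | Embolization | Control | Difference | Power |
|---|---|---|---|---|
| All SAEs, f = 25% | 16.1% | 12.7% | +3.4 | 0.25 |
| All SAEs, f = 50% | 17.1% | 15.4% | +1.7 | 0.09 |
| All SAEs, f = 100% | 19.25% | 20.8% | −1.55 | wrong direction |
| Without recurrence/progression | 15% | 10% | +5.0 | 0.53 |

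The last row assumes perfect attribution. It also treats the events removed as recurrence or progression: deaths that count as primary events would stay in the proposed row.

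**The case against.** The strongest reply is that the plan already shows procedural harm elsewhere. Table 7 has a row for major complications of embolization. Special-interest events are reported as assessed by both the Clinical Event Committee (CEC) and the investigator. Deaths are tabulated, and protocol 10.1.3 grades relation to the device. Much of this stands. A reader might infer that SAEs are tabulated only in total, or that the whole safety analysis conceals harm. The documents support neither: protocol 7.2.1 and SAP 9.2.2.1 plan tables by organ class and preferred term, and Table 7 plans listings.

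These outputs do not supply the missing count, however. The procedure rows stop at 30 days and cover listed events. The row combining drilling and embolization can itself fall when fewer patients are re-operated. The special-interest events are not defined in the available text. Patients are counted once, so subtracting a recurrence term from the total also removes patients who had both a recurrence and another SAE. Listings hold the data but are not a between-arm summary.

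A second reply is that fewer SAEs through fewer re-operations is a real gain for patients, not bias. That is right, and it is the reason to keep the total row.

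A third is that the overlap is below 100%, because hematoma growth without admission or operation need not be an SAE. That also stands, so the 7-point end of the range is an upper limit and not an expectation.

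A reader might also infer that an early recurrence counts among the 30-day complications, because "Symptomatic intracranial hemorrhage" lacks the surgery-related qualifier of the items around it. The item sits under a surgery- or procedure-related heading in both SAP 1.2 and Table 7, and no passage says that an unrelated recurrence counts there.

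**Conclusion.** The point holds for the total SAE rate. The protocol's SAE criteria and the primary endpoint overlap, and the available text plans no by-arm SAE count free of the overlap. The excess offset runs from about 1.5 points at 25% overlap to 7.0 at 100%. That range rests on the design rates of 12% and 5%, an assumed 5–15% of other SAEs and independence. The true overlap is unknown.

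The masking is partial. Fatal procedural harm within 90 days would also count against embolization on the primary endpoint, and the rows named above would show many listed early complications. Nothing here questions the sample size.

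One reservation: protocol 10.3 appears in the contents, but its text was not in the version examined, and the CEC constitution is a separate document. Either could contain a rule for expected disease events. SAP 9.2, which specifies the safety tables, has none.

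**What to change.** Keep the all-SAE row. Add to Table 7, by arm at 90 and 360 days, the number and percentage of patients with at least one SAE other than SDH recurrence or progression and the admission or operation for it. State in SAP 9.2.2 that:

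- attribution rests on CEC review, blinded to arm where possible;
- deaths and procedure-related bleeding stay in the count;
- the row supplements the total and does not replace it.

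The cost is two table entries and an attribution recorded for each SAE. Protocol 11.5 already sends protocol-specified safety endpoints to the CEC, and SAP 8.2.1 already determines primary events from surgery records, central imaging and Outcome Assessment Committee data. No new patient data are needed, and the primary analysis is unchanged. No passage says that each SAE will be attributed to recurrence or progression, so that step is new work. It needs judgement in an open-label trial, and a procedural bleed could be labelled a recurrence. Showing both rows lets the reader see what the attribution removed.

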
- Symptomatic SDH recurrence and progression rate within 90 days post-procedure

Symptomatic SDH recurrence refers to the maximum thickness of hematoma exceeding 10 mm combined with neurological symptoms, or the patient requires re-operation (surgery group);

Symptomatic SDH progression refers to the maximum thickness of hematoma increasing by more than 3 mm compared with baseline, or the patient requires operation (drug therapy group).

Secondary efficacy endpoints:

- Symptomatic SDH recurrence and progression rate at 360 days post-procedure
- Success rate of target vessel embolization (MMA trunk and branch vessels) on digital subtraction angiography (DSA) imaging
- Change in hematoma thickness on computed tomography (CT)/magnetic resonance imaging (MRI) at 90 days post-procedure
- Change in hematoma volume at 90 days post-procedure
- Change in midline shift on CT/MRI imaging at 90 days post-procedure
- Change in mRS score at 90 days and 360 days post-procedure
- Proportion of patients with mRS score ≤ 2 at 90 days and 360 days post-procedure
- Proportion of patients with mRS score ≤ 3 at 90 days and 360 days post-procedure
- Quality of life evaluated with EQ-5D Scale at 90 days and 360 days post-procedure

- Total hospital length of stay, number of re-hospitalizations, discharge location (home vs. rehabilitation hospital), and total hospitalization expenses

The safety endpoints in this study include:

- Serious adverse events (SAEs) within 90 days and 360 days;
- SDH-related mortality within 90 days and 360 days;
- Severe surgery-related complications within 30 days post-procedure (including surgery and embolization)
 - Symptomatic intracranial hemorrhage
 - Surgery-related intracranial hemorrhage
 - Surgery-related neurological deficits
 - Surgery-related central nervous system infection
 - Surgery-related arterial dissection, vascular wall injury, and vascular rupture and perforation
 - Surgery-related ischemia
 - Retroperitoneal/wrist hematoma
 - Neuropathy at the puncture site
 - Contrast allergy or contrast encephalopathy

Note: Follow-up time at 30 days, 90 days, and 360 days post-procedure will be calculated based on the day of randomization in this study. Relevant endpoint events and safety events will be collected at these follow ups.

3. Study Design

[figure not shown]

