6.5 Clinical Examination and Evaluation

(1) Inspection items before randomization include:

Routine blood work (red blood cell count, white blood cell count, platelet count, and hemoglobin);

Coagulation (activated partial thromboplastin time [APTT], INR);

Hepatic and renal function (alanine aminotransferase [ALT], aspartate aminotransferase [AST], blood urea nitrogen [BUN], creatinine [Cr]), electrolytes (potassium, sodium, chlorine, and fingerstick blood glucose);

Cranial CT scanning;

DSA;

Cranial MRI (depending on the conditions);

Urine human chorionic gonadotropin (HCG) test (female of childbearing age).

(2) Assess mRS score and EQ-5D score at screening and during baseline period;

(3) Total length of hospital stay, destination for rehabilitation after discharge, and total hospitalization expenses are recorded at discharge;

(4) Record severe surgery-related complications of subjects in 30 days after any surgical procedure (including burr-hole drainage and MMA embolization);

(5) Re-examine cranial CT/MRI at 90 days after randomization and record total hospital stay, re-hospitalization times, destination for rehabilitation after discharge, and total hospitalization expenses;

(6) Assess mRS score and EQ-5D score at 90 days and 360 days after randomization;

(7) Record SAEs, SDH-related death events, and severe surgery-related complications, total hospital length of stay, number of re-hospitalizations, destination for rehabilitation after discharge, and total hospitalization expenses at 30 days, 90 days and 360 days after randomization.

7. Statistical Analysis

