7.2 Safety Analysis

7.2.1 Adverse events

Adverse event (AE) data is described according to the current version of MedDRA and then statistically analyzed.

SAEs within 90 days and 360 days post-procedure and the incidence of serious surgery-related complications within 30 days after surgery are summarized. The incidence of AEs is recorded as 1 case if multiple AEs occur in one patient or the same AE occurs frequently in one patient.

AEs will be summarized by system organ class (SOC) and preferred term (PT) in a frequency table. The incidence is calculated by systems and symptoms/signs (count of cases: the number of subjects with at least one AE).

Severity of AEs: When the same subject has the same AE several times, the most serious one is used to analyze the severity of the AE.

A list of subjects experiencing AEs will be provided.

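### SAP Table 7 starts the 30-day complication window at randomization, while SAP 1.2 and protocol 7.2.1 start it at surgery, so complications of later operations drop out of the named endpoint

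*SAP*

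**What the plan says.** The plan gives the 30-day complication window more than one starting point.

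- **SAP Table 7** (planned safety displays): "Procedure-related serious complications within 30 days after randomization (including surgical and interventional procedures"), that is, from randomization.
- **SAP 1.2** (safety endpoints): "Severe surgery-related complications within 30 days after surgery (including trepanation/drainage and MMA embolization"), that is, from surgery.
- **Protocol 7.2.1**: "the incidence of serious surgery-related complications within 30 days after surgery are summarized", again from surgery.
- **Protocol 6.5(4)** (data collection): "Record severe surgery-related complications of subjects in 30 days after any surgical procedure (including burr-hole drainage and MMA embolization").
- **Protocol section 2** (safety endpoint list): "Severe surgery-related complications within 30 days post-procedure (including surgery and embolization"). The note below that list then says: "Follow-up time at 30 days, 90 days, and 360 days post-procedure will be calculated based on the day of randomization in this study".
- **Protocol 6.5(7)**: "Record SAEs, SDH-related death events, and severe surgery-related complications" at the 30-, 90- and 360-day visits.

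SAP 1.1 says that Table 1 summarizes every change from the protocol's analyses. Table 1 has no entry for this window.

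**The concern.** Two programmers working from these documents could produce different tables for the same named safety endpoint, one counting from randomization and the other from the procedure.

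The choice matters because index treatment is scheduled on day 0 (protocol Appendix 1). Complications of the index embolization or drainage therefore fall largely inside either window. Later operations are different: a re-operation, or a first operation in a patient who started on conservative treatment, can happen at any time in follow-up. Under the Table 7 wording, an operation on day 20 contributes 10 days of complication follow-up and one after day 30 contributes none.

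Later operations are also a component of the primary endpoint, which embolization is planned to reduce. If that effect is real, the Table 7 row counts the procedural harm of embolization almost in full and omits part of the harm of the operations it is meant to prevent.

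**Working it through.** **Step 1: the clocks side by side.**

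| Place | Window starts at |
|---|---|
| SAP Table 7 | randomization |
| Protocol section 2 list, read with its note | randomization, though labelled post-procedure |
| SAP 1.2 | surgery |
| Protocol 7.2.1 | surgery |
| Protocol 6.5(4) | any surgical procedure |

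Table 7 and the section 2 note are on one side; SAP 1.2 and protocol 6.5(4) and 7.2.1 are on the other. The conflict is already inside the protocol, and the SAP carries both versions.

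**Step 2: planned event counts.** The documents give no complication rate and no re-operation rate by arm. The only rates by arm are the planning rates for the primary endpoint (protocol 7.1.3 and SAP 3): 12% control, 5% embolization, two-sided alpha 0.05, power 90%, loss 8%, total 722.

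Reproducing 722 with the pooled-variance formula for two proportions:

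- mean rate = (0.12 + 0.05)/2 = 0.085
- n per arm = [1.960 × √(2 × 0.085 × 0.915) + 1.282 × √(0.12 × 0.88 + 0.05 × 0.95)]² / 0.07² = 332 after rounding up
- with loss: 332/0.92 = 361 per arm, total 722, an exact match

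Planned primary events per 361 patients:

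- control: 361 × 0.12 = 43.3
- embolization: 361 × 0.05 = 18.1
- control share: 43.3/61.4 = 71%

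On the 332 evaluable per arm, the counts are 39.8 and 16.6, with the same share.

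**Step 3: operations after day 30.** Two assumptions, neither in the documents: every planned primary event is an operation (the upper end), and operations are spread evenly over 90 days. Then 60/90 fall after day 30:

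- control: 43.3 × 2/3 = 29
- embolization: 18.1 × 2/3 = 12

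If half the events are operations, these become 14 and 6.

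**Step 4: complications missing from the row.** Assumed ranges: 25–100% of events are operations; 25–75% of those have their complication window beyond day 30; 5–20% have a severe complication.

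| | Control | Embolization | Difference, percentage points of 361 |
|---|---|---|---|
| Low (25%, 25%, 5%) | 43.3 × 0.25 × 0.25 × 0.05 = 0.14 | 18.1 × 0.25 × 0.25 × 0.05 = 0.06 | 0.02 |
| Middle (50%, 50%, 10%) | 1.08 | 0.45 | 0.17 |
| High (100%, 75%, 20%) | 43.3 × 0.75 × 0.20 = 6.5 | 18.1 × 0.75 × 0.20 = 2.7 | 1.05 |

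These counts cover operations up to day 90 only. Operations between days 90 and 360 would also fall outside the Table 7 window, but the planning rates do not cover them.

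**The case against.** The strongest reply is that Table 7 follows the protocol. The section 2 note sits directly under the list containing this endpoint and says that such times "will be calculated based on the day of randomization in this study". This stands: Table 7 is not simply at odds with the protocol. It does not settle the matter, because protocol 6.5(4) and 7.2.1 and SAP 1.2 still say otherwise.

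A second reply is that a randomization clock gives both arms the same fixed window, whereas a window reopened by each rescue operation depends on the efficacy outcome. That is a fair trade-off and a reason to show both counts.

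A third is that Table 7 is only an overview, so its row title may be loosely worded. That is plausible: its own footnote calls these postoperative complications, and its adverse event row runs from surgery. That row has the mirror problem, since a control who is never operated on has no start date. Loose wording still needs correcting before tables are programmed.

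A reader might go further and infer three things that the documents do not support:

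- **That late complications are lost.** Protocol 6.5(7) records them to day 360. Table 7 also plans 90- and 360-day displays of adverse events and serious adverse events, where they can appear. Those tables summarize by organ class and preferred term (SAP 9.2.2.1), so they do not replace the complication row.
- **That SAP 1.2 already promises a window for each procedure.** It says after surgery. Only protocol 6.5(4) refers to any procedure, and that is a collection instruction.
- **That the omissions fall mostly in controls.** This rests on the planned 12% versus 5% for a composite that also includes death and symptomatic thickness events without surgery. With equal rates the split is even.

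**Conclusion.** The inconsistency is certain: the row planned in Table 7 does not report the endpoint as SAP 1.2 defines it, and no change is declared. Taken literally, it omits complications of operations after day 30 and shortens the window for any procedure done after day 0.

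The size is uncertain and probably small. At the upper end, with all planned primary events taken as operations and even timing assumed, about 29 control and 12 embolization operations up to day 90 have no complication window. Under the assumed ranges, the between-arm difference in the complication rate changes by about 0.02 to 1.05 percentage points. A tilt against embolization follows only if the planned effect is real; it is not a demonstrated bias. The point is worth correcting because a named safety endpoint should have one definition and the correction is cheap.

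**What to change.** - In SAP Table 7, report serious procedure-related complications within 30 days of each drainage or embolization, including later operations. This matches SAP 1.2 and protocol 6.5(4) and 7.2.1. State in SAP 1.2 that a later operation opens its own window.
- Keep the count over 30 days from randomization as a second row, because the procedure-based window depends on whether a patient is operated on again.
- Show index and later procedures separately.
- Add to the protocol section 2 note that this endpoint runs from the procedure date, and record the clarification in SAP Table 1.
- While editing Table 7, give its adverse event row a start date that exists for every patient.

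The cost is wording and additional rows in one table. Protocol 6.5(4) already requires the data, assuming that procedure dates are held in the database. Changing the protocol note needs ethics committee approval under protocol 9.2.
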